### **9.3.2. Laboratory Value Summaries**

All test results and associated normal ranges from central laboratories will be reported in SI units. Any laboratory test results and associated normal ranges from local laboratories will be converted to SI units.

When there are multiple laboratory nonmissing values for a participant's particular test at a scheduled visit, central laboratory values have higher priority over local laboratory values. If a tie still exists, the laboratory value with the smallest laboratory sequence number will be used in by-visit summaries.

Numeric laboratory values will be summarized descriptively in SI units, and non-numeric test values will be tabulated when necessary. In addition, line graphs will be provided for ALT, AST, hemoglobin, platelet counts, leukocytes, neutrophils, and lymphocytes.

Shift tables will be presented showing change in CTCAE grade from baseline to worst grade postbaseline. Separate summaries for abnormally high and abnormally low laboratory values will be provided when the laboratory parameter has both high and low grading criteria. The denominator for the percentage calculation will be the number of participants in the baseline category. The number of participants who experienced worsening of laboratory abnormalities will be summarized by maximum postbaseline severity.

### **9.3.3. Potential Hy's Law Events**

Participants with elevated ALT or AST  $> 3 \times$  ULN range and alkaline phosphatase  $< 2 \times$  ULN range accompanied by total bilirubin  $> 2 \times$  ULN range at the same visit will be listed.

### **9.3.4. Worsening Laboratory Events of Special Interest**

Laboratory events of special interest are listed below.

- ALT increased
- AST increased
- Absolute neutrophil count decreased

The time to onset of a worsening laboratory event is defined as the interval between the date of first dose of study drug and the date of the first occurrence of CTC grade worse than baseline for the laboratory event. Participants who have not experienced a worsening laboratory event at the time of analysis will be right-censored at the last postbaseline study visit with nonmissing CTC grade of the laboratory event.

Time to onset of worsening Grade 3 or 4 laboratory events of special interest will be summarized using descriptive statistics and the life-table method as described in Section 9.2.2, and the Kaplan-Meier plot of time to onset of worsening Grade 3 or 4 absolute neutrophil count decreased will be provided. Laboratory events of special interest to be summarized may be adjusted based on emerging data.

## 9.4. Vital Signs

Values at each scheduled visit, change, and percentage change from baseline for vital signs, including weight, systolic blood pressure, diastolic blood pressure, pulse, body temperature, and respiratory rate will be summarized descriptively.

Normal ranges for vital sign values are defined in [Table 4](#). The abnormal values for participants exhibiting vital sign abnormalities will be listed along with their assigned treatment regimen.

Alert vital signs are defined as an absolute value outside the defined normal range and percentage change greater than 25%. Note that the definition of alert vital signs does not apply for body temperature and weight. The abnormal values for participants exhibiting alert vital sign abnormalities will be listed.

**Table 4: Normal Ranges for Vital Sign Values**

Parameter	High Threshold	Low Threshold
Systolic blood pressure	≤ 155 mmHg	≥ 85 mmHg
Diastolic blood pressure	≤ 100 mmHg	≥ 40 mmHg
Pulse	≤ 100 bpm	≥ 45 bpm
Temperature	≤ 38°C	≥ 35°C
Respiratory rate	≤ 24 breaths/min	≥ 12 breaths/min

## 9.5. Electrocardiograms

Twelve-lead ECGs including PR, QRS, QT, QTcB, QTcF, and RR intervals will be obtained for each participant during the study. Values at each scheduled visit, change, and percentage change from baseline will be summarized for each ECG parameter. Baseline will be determined as the average of all nonmissing values before the first administration of pascalisib.

Normal ranges for ECG values are defined in [Table 5](#). Electrocardiogram values will also be considered abnormal if the absolute percentage change from baseline is more than 25% (30% for QRS interval). Participants exhibiting ECG abnormalities will be listed with study visit and assigned treatment regimen. Abnormal values for participants with alert ECG values, defined as both the absolute value and the percentage change from baseline being outside normal ranges, will be identified and listed. Outliers of QT, QTcB, and QTcF values, defined as absolute values > 450 milliseconds or change from baseline > 30 milliseconds, will be summarized.

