12. Current or previous other malignancy within 3 years of study entry, except cured basal or squamous cell skin cancer, superficial bladder cancer, prostate intraepithelial neoplasm, carcinoma in situ of the cervix, or other noninvasive or indolent malignancy without sponsor approval.
13. History of stroke or intracranial hemorrhage within 6 months of the date of study treatment administration.
14. Chronic or current active infectious disease requiring systemic antibiotics, antifungal, or antiviral treatment, and exposure to a live vaccine within 30 days of study treatment administration.
15. Known HIV infection or positivity.
16. Hepatitis B (HBV) or HCV infection: Participants positive for HBsAg or hepatitis B core antibody will be eligible if they are negative for HBV-DNA; these participants should be considered for prophylactic antiviral therapy. Participants positive for anti-HCV antibody will be eligible if they are negative for HCV-RNA.
17. Clinically significant cardiac disease, including unstable angina, acute myocardial infarction, and or cardiac conduction issues within 6 months of the date of study treatment administration.

18. Current New York Heart Association Class II to IV congestive heart failure or uncontrolled arrhythmia.
19. Presence of an abnormal ECG that is clinically meaningful. Screening QTc interval > 450 milliseconds is excluded (corrected by Fridericia). In the event that a single QTc is > 450 milliseconds, the participant may enroll if the average QTc for 3 ECGs is < 450 milliseconds.
20. Unable to swallow and retain oral medication, malabsorption syndrome, disease significantly affecting gastrointestinal function, total resection of the stomach or small bowel, ulcerative colitis, symptomatic inflammatory bowel disease, or partial or complete bowel obstruction.
21. Known hypersensitivity or severe reaction to pascalisib (**IB**) or any of the excipients.
22. History of serious allergic reactions including anaphylaxis and toxic epidermal necrolysis.
23. Inadequate recovery from toxicity and/or complications from a major surgery before study treatment administration.
24. Currently pregnant or breastfeeding.
25. Any condition that would, in the investigator's judgment, interfere with full participation in the study, including administration of study treatment and attending required study visits; pose a significant risk to the participant; or interfere with interpretation of study data.

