8.3.4. Electrocardiograms

12-lead ECG will be obtained as outlined in the SoA (see Table 3). All 12-lead ECGs will be performed with the participant in a recumbent or semirecumbent position after 5 minutes of rest. Baseline ECGs will be obtained during screening using a single measurement but can be performed in triplicate if the single QTc measurement is > 450 milliseconds (corrected by Fridericia; see Section 5.2).

Electrocardiograms will also be obtained during the Day 1 visit (triplicate measurements) before the participant receives the first dose of study drug. Triplicate ECGs will be performed predose

and 1.5 hours (\pm 15 minutes) after receiving study treatment at the Week 4 visit. When triplicate ECGs are being obtained, individual measurements should be performed 5 minutes (\pm 3 minutes) apart. All 12-lead ECGs obtained at subsequent timepoints (single measurements) will be compared with the baseline 12-lead ECGs as follows:

- For ECG morphology, all postdose ECG recordings will be compared with Day 1 predose ECGs.
- For the calculation of changes in cardiac intervals (eg, QT interval), the intervals from the screening and Day 1 predose (triplicate) ECGs will be computed and averaged and used as the baseline for comparison of all postdose intervals.

If a single measurement demonstrates a QTc interval $>$ 500 milliseconds, 2 more ECGs should be obtained over a brief period, and the averaged QTc intervals should be used to determine whether the study treatment should be interrupted.

Twelve-lead ECGs will be acquired using an ECG analysis system with analysis and printing capabilities. The 12-lead ECGs will be interpreted by the investigator at the site and will be used for immediate participant management. The decision to include or exclude a participant or discontinue a participant's participation in the study based on an ECG is the responsibility of the investigator, in consultation with the sponsor's medical monitor, as appropriate. Twelve-lead ECGs that are identified by the investigator as "Abnormal, Clinically Significant" will be sent to the sponsor's medical monitor for review.

Electrocardiogram abnormalities where study exclusion, further cardiovascular investigation, and/or prompt action may be necessary depending on the clinical context.

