**Table 5: Normal Ranges for Electrocardiogram Values**

Parameter	High Threshold	Low Threshold
PR	≤ 220 ms	≥ 75 ms
QRS	≤ 120 ms	≥ 50 ms
QT	≤ 500 ms	≥ 300 ms
QTcB, QTcF	≤ 450 ms	≥ 295 ms
RR	≤ 1330 ms	≥ 600 ms

QTcB = Bazett's correction; QTcF = Fridericia's correction.

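### For a baseline QTc above 400 ms, the SAP's ECG alert listing can omit values over the protocol's 500 ms trigger, and the outlier definition does not count them separately (a minor reporting gap)

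*SAP*

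**What the plan says.** SAP 9.5 sorts ECG values into three groups.

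- **Abnormal:** outside the Table 5 range (295 to 450 ms for QTcB and QTcF), or where the "absolute percentage change from baseline is more than 25% (30% for QRS interval"). Participants with such values are listed by visit.
- **Alert:** "defined as both the absolute value and the percentage change from baseline being outside normal ranges". Both conditions must hold. These values go to Listing 2.10.3.
- **Outlier (QT, QTcB, QTcF):** above 450 ms, or a rise of more than 30 ms from baseline. These are summarised in Table 3.5.8.

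On baseline, SAP 9.5 states: "Baseline will be determined as the average of all nonmissing values before the first administration of pascalisib".

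Protocol 8.3.4 sets a different level. When a single QTc exceeds 500 ms, "2 more ECGs should be obtained over a brief period, and the averaged QTc intervals should be used" in deciding whether to interrupt treatment. On entry, exclusion criterion 19 in Protocol 5.2 reads "Screening QTc interval > 450 milliseconds is excluded (corrected by Fridericia"), with a provision for averaging three ECGs when a single value is too high.

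**The concern.** The alert is the SAP's most selective ECG flag, yet it is not tied to the one QTc level on which the protocol acts during the study. Because the rule requires a proportional change as well as an out-of-range value, the QTc needed for an alert rises with baseline. Participants who start closest to 500 ms are therefore the least readily flagged when they pass it.

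The outlier definition does not fill the gap, since its only absolute cut is 450 ms. Under that definition 451 ms and 520 ms fall in the same class. Someone who reads Listing 2.10.3 and Table 3.5.8 alone could find no QTc alert and no separate count, although the protocol's own trigger had been crossed.

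**Working it through.** The documents give no derived figure for this rule, so there is none to reproduce. The check is direct arithmetic.

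**Inputs**

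- Upper limit of the QTc range: 450 ms (SAP Table 5).
- Percentage limit for QTc: more than 25% (SAP 9.5; the 30% limit is for QRS only).
- Protocol trigger: QTc above 500 ms (Protocol 8.3.4).
- Entry: screening QTcF up to 450 ms is not excluded (Protocol 5.2, criterion 19).

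**Alert level.** With baseline *B*, a high QTc is an alert only if QTc > 450 and (QTc − *B*)/*B* > 0.25. That is the same as QTc > max(450, 1.25 × *B*).

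**Crossover.** Setting 1.25 × *B* = 500 gives *B* = 500/1.25 = 400 ms. At or below 400 ms, every QTc above 500 ms is an alert. Above 400 ms, values from just over 500 ms up to 1.25 × *B* are not. The width of that band is 1.25 × *B* − 500.

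| Baseline (ms) | Alert only above (ms) | Band over 500 ms without an alert (ms) | Change at 501 ms |
|---|---|---|---|
| 360 | 450 | 0 | +39.2% |
| 380 | 475 | 0 | +31.8% |
| 400 | 500 | 0 | +25.3% |
| 401 | 501.25 | 1.25 | +24.9% |
| 410 | 512.5 | 12.5 | +22.2% |
| 420 | 525 | 25 | +19.3% |
| 430 | 537.5 | 37.5 | +16.5% |
| 440 | 550 | 50 | +13.9% |
| 450 | 562.5 | 62.5 | +11.3% |

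**Worked case.** From 430 to 520 ms the rise is 90 ms, and 90/430 = 20.9%.

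- Protocol trigger: crossed (520 > 500).
- Abnormal: yes (520 > 450), so in Listing 2.10.2.
- Outlier: yes, on both cuts (520 > 450 and 90 > 30), so in Table 3.5.8.
- Alert: no (20.9% is below 25%), so not in Listing 2.10.3.

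**What a plain 500 ms rule would lose.** Replacing the present rule with QTcF above 500 ms would drop alerts that it now raises:

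- 370 to 480 ms: 110/370 = +29.7%, and 480 > 450. An alert now, not one under the replacement.
- 360 to 455 ms: 95/360 = +26.4%, and 455 > 450. The same.
- Low side: 400 to 290 ms is −110/400 = −27.5%, and 290 < 295. An alert now, not one under the replacement.

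**The case against.** The strongest reply is that nothing goes unreported. Any QTc above 500 ms is above 450 ms, so it appears among all ECG values (Listing 2.10.1), among the abnormal values (Listing 2.10.2) and as an outlier in Table 3.5.8. Table 3.5.9 also summarises clinically significant ECG abnormalities, and Protocol 9.1 has clinically significant ECG findings reported as adverse events. On-study handling follows Protocol 8.3.4 at the site and does not wait for an analysis listing. All of this stands, and it is why the point is minor.

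A reader might infer that the report would hide QTc prolongation or that participants would be put at risk. The documents support neither. What is missing is the alert label and a separate count. Nor does the rule miss every QTc above 500 ms when baseline is over 400 ms: values above 1.25 times baseline are still alerts.

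It can also be said that no document requires the two levels to match, and that SAP 9.4 uses the same kind of rule (out of range plus a change above 25%) for vital signs. That explains where the rule may come from. It does not make a percentage filter informative for QTc, where the protocol has already named an absolute level.

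Two limits on what can be seen also apply. The protocol's table of notable ECG criteria (Section 10.4.4.4, Table 13) is named in the amendment summary but is not in the text reviewed, so the SAP rule cannot be compared with it. The layout of Table 3.5.8 is in a separate document. That 451 and 520 ms count alike therefore follows from the SAP's outlier definition, not from the table itself.

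**Conclusion.** The point holds as a minor gap in safety reporting. For baselines above 400 ms, QTc values from just over 500 ms up to 1.25 times baseline cross the protocol's trigger without entering the alert listing, and the SAP's outlier definition gives them no category of their own. The band is 1.25 ms wide at a baseline of 401 ms, 25 ms at 420 ms and 62.5 ms at 450 ms. The documents give no QTc distribution, so the number of the approximately 40 participants who might fall in it cannot be estimated.

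The conclusion assumes that the percentage limit in the alert rule is the 25% in the sentence before it. Table 5 gives no percentage range, and the text supports no other reading. It also assumes that baselines between 400 and 450 ms occur, which eligibility allows. Neither the primary endpoint nor any clinical rule is affected.

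**What to change.** In SAP 9.5, keep the current alert rule for all parameters and add one condition: a value is also an alert if QTcF exceeds 500 ms, whatever the percentage change. State whether the same applies to QTcB. Add an above-500 ms category to the outlier definition and to Table 3.5.8.

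Do not remove the 25% rule. As the working shows, that would lose alerts now raised between 450 and 500 ms and on the low side.

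The change reuses the protocol's existing 500 ms level for reporting only. It costs a little SAP wording, one listing filter and one table row, with no new data. The downside is a few more listed values.

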**Table 5: Normal Ranges for Electrocardiogram Values**

Parameter	High Threshold	Low Threshold
PR	≤ 220 ms	≥ 75 ms
QRS	≤ 120 ms	≥ 50 ms
QT	≤ 500 ms	≥ 300 ms
QTcB, QTcF	≤ 450 ms	≥ 295 ms
RR	≤ 1330 ms	≥ 600 ms

QTcB = Bazett's correction; QTcF = Fridericia's correction.

## 10. INTERIM ANALYSES

An interim futility analysis is planned when the first 20 participants have been evaluated for response or have been followed for at least 9 weeks or have permanently discontinued study treatment because of disease progression, withdrawal of consent, or death. The study will be terminated for futility if  $\leq 7$  of the 20 participants have responded (ie, CR or PR) based on assessments provided by the IRC; otherwise the study will continue. The probability of stopping at interim for futility is 60.10% when the true response rate is 35% or 1.32% when the true response rate is 62%.

An IDMC will be charged with evaluating interim futility results. The IDMC will consist of clinicians and an independent statistician. The IDMC will make recommendations to the sponsor at the planned interim futility analysis. The process by which the IDMC will make recommendations and decisions will be documented in the IDMC charter. Additional operational details of the interim analyses, including tables, figures, and listings provided to the IDMC, will be provided in the IDMC Charter.

There is no efficacy interim analysis planned for the study as there are no plans to stop the study early for overwhelming efficacy.

## 11. CHANGES AND MODIFICATIONS TO THE ANALYSIS PLAN

All versions of the SAP are listed in [Table 6](#).

**Table 6: Statistical Analysis Plan Versions**

SAP Version	Date
Original	22 MAR 2021
Amendment 1	26 JAN 2023

### 11.1. Changes to Protocol-Defined Analyses

Not applicable.

### 11.2. Changes to the Statistical Analysis Plan

#### Amendment 1 (26 JAN 2023):

**Overall Rationale for the Amendment:** The minimum observation period required for evaluation of the primary endpoint (ORR) was updated based on the time to response data from a non-Japanese study. This modification led to the SAP Amendment 1 reflecting this change.

- Section 7.3 has been modified to include the timing of the primary analysis.

## APPENDIX A. PLANNED TABLES, FIGURES, AND LISTINGS

This appendix provides a list of the planned tables, figures, and listings for the Clinical Study Report. Standard tables will follow the conventions in the Standard Safety Tables v1.10. Shells are provided for nonstandard tables in a separate document.

The lists of tables, figures, and listings and the shells are to be used as guidelines. Modifications of the lists that do not otherwise affect the nature of the analysis will not warrant an amendment to the SAP.

### Tables

Table No.	Title	Population	Standard
Baseline and Demographic Characteristics			
1.1.1	Analysis Populations	All-Screened	X
1.1.2	Summary of Participant Disposition	FAS	X
1.1.3	Summary of Number of Participants Enrolled by Site	FAS	X
1.1.4	Summary of Protocol Deviations	FAS	X
1.2.1	Summary of Demographics and Baseline Characteristics	FAS	X
1.3.1	Summary of Baseline Disease Characteristics	FAS	X
1.3.2	Summary of Prior Cancer Therapy	FAS	
1.3.3	Summary of Prior Systematic Cancer Therapy by WHO Drug Class and Preferred Term	FAS	
1.4.1	Summary of Prior Medications	FAS	X
1.4.2	Summary of Concomitant Medications	FAS	X
1.5.1	Summary of General Medical History	FAS	X
Efficacy			
2.1.1	Summary of Best Overall Response and Objective/Complete Response Rate as Determined by Independent Review Committee	FAS	
2.1.2	Summary of Best Overall Response and Objective/Complete Response Rate as Reported by Investigator	FAS	
2.1.3	Summary of Best Overall Response and Objective Response Rate as Determined by Independent Review Committee by Subgroup	FAS	
2.2.1	Summary of Duration of Response as Determined by Independent Review Committee	FAS	
2.2.2	Summary of Duration of Response as Reported by Investigator	FAS	
2.2.3	Summary of Progression-Free Survival as Determined by Independent Review Committee	FAS	
2.2.4	Summary of Progression-Free Survival as Reported by Investigator	FAS	
2.2.5	Summary of Overall Survival	FAS	
2.2.6	Summary of Best Change in Target Lesion Size as Determined by Independent Review Committee	FAS	
2.2.7	Summary of Best Change in Target Lesion Size as Reported by Investigator	FAS	

Table No.	Title	Population	Standard
Safety			
3.1.1	Summary of Exposure and Compliance	Safety	
3.1.2	Summary of Exposure and Average Daily Dose During Initial QD and Maintenance Dosing Periods	Safety	
3.2.1	Overall Summary of Treatment-Emergent Adverse Events	Safety	X
3.2.2	Summary of Treatment-Emergent Adverse Events by MedDRA System Organ Class and Preferred Term	Safety	X
3.2.3	Summary of Treatment-Emergent Adverse Events by MedDRA Preferred Term in Decreasing Order of Frequency	Safety	X
3.2.4	Summary of Treatment-Emergent Adverse Events by MedDRA System Organ Class, Preferred Term, and Maximum Severity	Safety	X
3.2.6	Summary of Grade 3 or Higher Treatment-Emergent Adverse Events by MedDRA System Organ Class and Preferred Term	Safety	X
3.2.7	Summary of Grade 3 or Higher Treatment-Emergent Adverse Events by Preferred Term in Decreasing Order of Frequency	Safety	X
3.2.8	Summary of Serious Treatment-Emergent Adverse Events by MedDRA System Organ Class and Preferred Term	Safety	X
3.2.9	Summary of Serious Treatment-Emergent Adverse Events by Preferred Term in Decreasing Order of Frequency	Safety	X
3.2.10	Summary of Parsaclisib Treatment-Related Treatment-Emergent Adverse Events by MedDRA System Organ Class and Preferred Term	Safety	X
3.2.11	Summary of Parsaclisib Treatment-Related Treatment-Emergent Adverse Events by MedDRA Preferred Term in Decreasing Order of Frequency	Safety	X
3.2.12	Summary of Parsaclisib Treatment-Related Treatment-Emergent Adverse Events by MedDRA System Organ Class, Preferred Term, and Maximum Severity	Safety	X
3.2.14	Summary of Grade 3 or Higher Parsaclisib Treatment-Related Treatment-Emergent Adverse Events by MedDRA System Organ Class and Preferred Term	Safety	X
3.2.15	Summary of Parsaclisib Treatment-Related Serious Treatment-Emergent Adverse Events by MedDRA System Organ Class and Preferred Term	Safety	X
3.2.16	Summary of Treatment-Emergent Adverse Events With a Fatal Outcome by MedDRA System Organ Class and Preferred Term	Safety	X
3.2.18	Summary of Treatment-Emergent Adverse Events Leading to Parsaclisib Dose Reduction by MedDRA System Organ Class and Preferred Term	Safety	X
3.2.19	Summary of Treatment-Emergent Adverse Events Leading to Parsaclisib Dose Interruption by MedDRA System Organ Class and Preferred Term	Safety	X
3.2.20	Summary of Treatment-Emergent Adverse Events Leading to Discontinuation of Parsaclisib by MedDRA System Organ Class and Preferred Term	Safety	X
3.2.25	Summary of Treatment-Emergent Adverse Events by MedDRA Preferred Term and Maximum Severity in Decreasing Order of Frequency	Safety	

Table No.	Title	Population	Standard
3.2.26	Summary of Selected Treatment-Emergent Adverse Events of Special Interest by Maximum Severity	Safety	
3.2.27	Summary of Time to Onset of Selected Treatment-Emergent Adverse Events of Special Interest	Safety	
3.2.28	Summary of Time to Onset of Selected Treatment-Emergent Adverse Events of Special Interest: Life-Table Method	Safety	
3.2.29	Summary of Longest Duration of Selected Treatment-Emergent Adverse Events of Special Interest	Safety	
3.3.1.1	Summary of Laboratory Values - Hematology	Safety	X
3.3.1.2	Summary of Laboratory Values - Chemistry	Safety	X
3.3.3.1	Shift Summary of Hematology Laboratory Values in CTC Grade - To the Worst Abnormal Value	Safety	X
3.3.3.2	Shift Summary of Chemistry Laboratory Values in CTC Grade - To the Worst Abnormal Value	Safety	X
3.3.3.4	Treatment-Emergent Worsening of Laboratory Abnormalities - Hematology	Safety	X
3.3.3.5	Treatment-Emergent Worsening of Laboratory Abnormalities - Chemistry	Safety	X
3.3.6	Time to Onset of Treatment-Emergent Worsening of Laboratory Events of Special Interest	Safety	
3.3.7	Time to Onset of Treatment-Emergent Worsening of Laboratory Events of Special Interest: Life-Table Method	Safety	
3.4.1	Summary of Systolic Blood Pressure	Safety	X
3.4.2	Summary of Diastolic Blood Pressure	Safety	X
3.4.3	Summary of Pulse	Safety	X
3.4.4	Summary of Respiratory Rate	Safety	X
3.4.5	Summary of Body Temperature	Safety	X
3.4.6	Summary of Weight	Safety	X
3.5.1	Summary of PR Interval (ms) From 12-Lead ECG	Safety	X
3.5.2	Summary of QRS Interval (ms) From 12-Lead ECG	Safety	X
3.5.3	Summary of QT Interval (ms) From 12-Lead ECG	Safety	X
3.5.4	Summary of QTcB Interval (ms) From 12-Lead ECG	Safety	X
3.5.5	Summary of QTcF Interval (ms) From 12-Lead ECG	Safety	X
3.5.6	Summary of RR Interval (ms) From 12-Lead ECG	Safety	X
3.5.8	Summary of Outliers of QT, QTcB, and QTcF Interval Values From 12-Lead ECG	Safety	X
3.5.9	Summary of Clinically Significant ECG Abnormality	Safety	X

